## Methods

Twenty-five patients with surgically resectable stage IB-IIIB ALK-rearranged NSCLC patients will be enrolled. These patients will receive lorlatinib neoadjuvant therapy for 6-8 weeks (determined by clinicians' decision based on clinical practice) and then underwent surgery. Eligible patients will be registered to receive oral lorlatinib 100mg qd for 6-8 weeks each during the neoadjuvant therapy phase. Neoadjuvant treatment response that will be assessed by the investigator using RECIST v1.1. If no progressive disease will be documented, candidates will undergo surgery with radical intent within 6 weeks after the completion of lorlatinib neoadjuvant therapy. Once patient complete surgery and pathological evaluation, she/he will remove from this study (within 1 month after surgery) and continue to receive treatment according to clinicians' decision based on clinical practice. All patients signed an informed consent prior to enrolment. Data will not be collected once patient withdrawal from this study.

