Lorlatinib will be administered orally QD at approximately the same time of the day on a continuous daily dosing schedule, ie, without a break in dosing in the absence of drug-related toxicity. Patients must swallow the study medication whole and must not manipulate or chew the medication prior to swallowing. Patients should be instructed to take their medication at approximately the same time every day. A dosing card will be provided to the patients to provide guidance for the correct use of lorlatinib. Patients must be instructed that should they miss a dose or vomit any time after taking a dose, they must not “make it up” with an extra dose. Instead, resume the subsequent doses as originally prescribed. Any missed dose may be taken up to 6 hours prior to the next scheduled dose, otherwise it should be skipped and dosing resumed with subsequent doses as prescribed. The patient must be instructed to record all doses (including missed or vomited) in a dosing diary supplied by the site. If doses are missed or vomited, this must be indicated in the source documents and Case Record Forms (CRFs).

The response to neoadjuvant therapy will be evaluated by the investigators utilizing RECIST 1.1 criteria. Patients demonstrating no progressive disease as per these criteria will proceed to surgical resection with radical intent, scheduled within 6 weeks following the conclusion of lorlatinib neoadjuvant therapy. Patients completing the surgical intervention and pathological evaluation will conclude their participation in this study within 1-month post-surgery and may continue to receive subsequent treatment as deemed appropriate by their healthcare providers, based on prevailing clinical practice.

This study will intermittently collect blood specimens from patients at baseline, during neoadjuvant therapy, and perioperatively to explore changes in tumor biomarkers. Baseline and postoperative tissue specimens will be obtained, and Whole Exome Sequencing (WES) will be performed to investigate the correlation between neoadjuvant therapy efficacy and tissue mutation changes. Additionally, tissue

mutation results will be used to customize a blood testing panel to enhance detection rates.

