Informed consent will be obtained from all participants prior to study enrollment. The consent process will ensure that patients are fully aware of the study's nature, its objectives, the investigational therapy involved, and the potential risks and benefits of participation. The study emphasizes rigorous adherence to ethical standards and patient safety, with a comprehensive plan in place for monitoring adverse events and implementing dose adjustments as necessary to manage toxicity.

Subjects will be on therapy until complete surgery and pathological evaluation, withdrawal of consent, death, or investigator decision dictated by protocol compliance, whichever occurs first. At the time of termination of study treatment, the patients could continue to receive treatment according to clinicians' decision in their clinical practice.

This study will take 18 months to enroll subjects, and each subject will be followed up for efficacy and safety during neoadjuvant process and 1-month post-surgery. Dose reduction information for management of AEs is included in Section 5.

Safety and efficacy assessments were performed throughout the treatment period and at the end-of-study visit. Routine safety assessments included the collection and evaluation of AEs, concomitant medications, vital signs, and body weight. Particular attention was given to AEs consistent with the lorlatinib toxicity profile (including lipid elevation, cognitive and mood disorder, etc.). Additional safety assessments performed at selected visits included ECOG PS, clinical laboratory tests, ECGs.

Safety assessments and efficacy assessments will be performed throughout the study as described in the Schedule of Activities (Table 1).

Study Activity	Screening & baseline ≤28 days of start of treatment	Cycle 1 Week 1-4	Cycle 2 Week 5-8	End of neoadjuvant (pre-surgery assessment)	End of treatment visit (Surgery complete)	Final follow-up visit (1 month after surgery)
Visits		Day 1	Day -4±2 day			
Informed consent 	X					
Medical history and demographics 	X					
ALK+ status	X					
Physical examination	X					
ECOG PS 	X	X	X	X	X	X
Brain scan MRI or CT 	X					
Vital signs  , Body weight, Height 	X	X	X	X	X	X
ECG 	X	X	X	X		X
Laboratory 						
Hematology 	X	X	X	X	X	X
Blood chemistry 	X	X	X	X	X	X
Urinalysis 	X	X	X	X	X	X
Pregnancy test 	X				(X)	

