13. Adverse event assessment includes tumor-related, treatment-related and unrelated signs and symptoms. The reporting period for non-serious AEs starts from the time the subject has taken the first dose of study treatment and ends at last subject visit or upon initiation of a subsequent anticancer treatment, whichever occurs first. The reporting period for serious AEs starts once a subject provides informed consent and ends 28 days after the last dose of study treatment irrespective of the start of

any subsequent anticancer treatment. Subjects must be followed for AEs at Post-Treatment Follow-up Visit at least 28 (and no more than 35) days after the end of treatment, or until all drug-related toxicities have resolved or are deemed irreversible, whichever is later. The National Cancer Institute Common Terminology Criteria for Adverse Events, Version 5.0 (CTCAE v5.0) will be used to grade AE severity.

14. Tumor assessments will include: PET/CT, or through computed tomography (CT), abdominal ultrasound, cranial MRI/CT, and bone scintigraphy at screening, in order to determine the accurate TNM staging. Physical examination for peripheral adenopathy or skin/subcutaneous nodules representing target measurable (by caliper) disease, if any are present.. Imaging serves also as safety assessment to monitor/exclude pulmonary toxicity. Chest X-ray will be performed on the first postoperative day to assess the surgical outcome and any procedural events. A chest X-ray will be conducted one month postoperatively to evaluate postoperative pulmonary recovery, including the presence of pleural effusion.
15. Subject Status Follow-up for Survival: Repeat tumor assessments are suggested to be done approximately every 4 weeks from the date of CT/MRI at the end of study treatment. Telephone contact approximately every cycle from post treatment follow-up visit to obtain regular follow-up is recommended. The information collected for subsequent therapies should include enumeration of the post-study treatment, including drugs administered, and date of initiation and discontinuation of each drug; and will be recorded in the CRF.

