#### **6.4.7 Follow-up**

Subjects should be followed up until 1 month after surgical treatment. Telephone contact or other means to obtain timely regular follow-up is recommended. The

information for subsequent therapies collected and recorded on the CRF should include drugs administered, date of initiation and discontinuation of each medication.

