## **8.1 Reporting Period**

For SAEs, the active reporting period to the investigator or its designated representative begins from the time that the subject provides informed consent, which is obtained prior to the subject's participation in the study, i.e., prior to undergoing any study-related procedures and/or receiving investigational product, through and including 28 calendar days after the last administration of the investigational product regardless of the start of any subsequent cancer therapy. SAE should be reported via the CRF in the active reporting period. Following the active safety reporting period, other SAEs of which the investigator becomes aware should be reported to drug provider, unless the SAE is attributed by the investigator to complications of either the underlying malignancy or any subsequent anti-cancer therapy or to the patient's participation in a subsequent clinical study.

Non-serious adverse events should be recorded on the CRF from the time the subject has taken at least one dose of study treatment through last subject visit.

If a subject begins a new anticancer therapy, the AE reporting period for non-serious AEs ends at the time the new treatment is started.

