### **8.11.2 Non-Serious Adverse Event Reporting Requirements**

Non-serious adverse events should be recorded on the CRF from the time the subject has taken at least one dose of study treatment through last subject visit.

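### Non-serious AE recording stops when new anticancer therapy starts, which conflicts with the scheduled one-month AE collection and can shorten the post-surgical window for some patients

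*Protocol*

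**What the plan says.** Two places end non-serious AE recording early. Section 8.1: "If a subject begins a new anticancer therapy, the AE reporting period for non-serious AEs ends at the time the new treatment is started". Table 1, footnote 13 (Section 3.1), says the period "ends at last subject visit or upon initiation of a subsequent anticancer treatment, whichever occurs first". Section 8.11.2 gives only the general rule, "from the time the subject has taken at least one dose of study treatment through last subject visit", which also stands in Section 8.1 just before the exception.

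After surgery, Section 3.1 says patients "may continue to receive subsequent treatment as deemed appropriate by their healthcare providers". The Methods part of the synopsis says the same in substance. Neither sets an earliest date.

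On the length of follow-up, Section 3.1 says "each subject will be followed up for efficacy and safety during neoadjuvant process and 1-month post-surgery" and Section 6.4.7 says "Subjects should be followed up until 1 month after surgical treatment". Table 1 has a final visit one month after surgery with the adverse event row marked. Section 6.4.6 requires a safety visit 28 to 35 days after the end-of-treatment visit for subjects who continue therapy after surgery, and lists both subsequent cancer therapy and AE review. Against these, Section 3.1 also says patients "will conclude their participation in this study within 1-month post-surgery", and the synopsis uses the same preposition.

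Surgical complication rate and safety and tolerability are both secondary endpoints (Section 2.2).

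**The concern.** Ending AE recording at the next anticancer drug is a familiar way to keep later toxicity out of a drug's safety profile. It fits poorly in a trial with an operation between the study drug and the next treatment. The events of interest in the month after surgery include complications of the operation, and these do not stop being relevant when adjuvant therapy starts.

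Sections 9.2.5 and 9.3 summarise safety by frequency and percentage. A crude percentage treats every patient as observed for the same time. If some patients are observed for two or three weeks after surgery and others for a month, the percentage mixes unequal windows, and the shorter ones can only lose events.

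Sites also receive conflicting instructions. For a patient who has started therapy before the one-month visit, Section 8.1 closes non-serious recording, while Table 1 and Section 6.4.6 ask for it. Different sites may resolve this differently.

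**Working it through.** The plan states no figure on this point, so there is none to reproduce. The check compares the windows and then does simple date arithmetic.

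**1. Instructions for a patient who starts new therapy before the one-month visit**

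- Section 8.1 and footnote 13, reporting-period sentence: non-serious recording has ended.
- Table 1, final visit column: collect AEs.
- Section 6.4.6: if therapy continues after surgery, review AEs 28 to 35 days after the end-of-treatment visit. Table 1 places that visit at completion of surgery, so this falls about one month after the operation.
- Footnote 13, later sentence: follow for AEs at a visit 28 to 35 days after end of treatment, or until drug-related toxicity resolves or is deemed irreversible, whichever is later.

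The first instruction cannot be followed together with the others unless post-operative therapy does not count as new or subsequent therapy. The protocol does not say whether it counts.

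**2. Non-serious cover after surgery**

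Let t be the post-operative day on which new therapy starts, and take one month as 30 days. Under Section 8.1, cover = min(t, 30).

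- No new therapy before the visit: 30 days.
- t = 21: 21 days.
- t = 14: 14 days.

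The values of t are assumptions.

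**3. Whether SAE reporting fills the gap**

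SAE reporting is not cut by new therapy, but it excludes non-serious events by definition. Its active period ends 28 days after the last dose (Section 8.1), and surgery may follow up to 6 weeks, or 42 days, after treatment ends (Section 3.1). With g days from last dose to surgery, active SAE cover after surgery is 28 − g:

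- g = 0: 28 days
- g = 14: 14 days
- g = 21: 7 days
- g = 28: 0 days
- g = 42: closed 14 days before surgery

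Later SAEs are reported only if the investigator becomes aware of them, with stated exceptions. The SAE stream does not replace the missing records.

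**4. Illustration of size, on assumptions that are not in the protocol**

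Suppose a true 30-day rate R of non-serious complications of 20% or 40%, a constant hazard, and a start of therapy unrelated to complications. A patient stopped at day t is then recorded with an event with probability 1 − (1 − R)^(t/30).

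- t = 14: 1 − 0.8^(14/30) = 9.9%; 1 − 0.6^(14/30) = 21.2%
- t = 21: 1 − 0.8^(21/30) = 14.5%; 1 − 0.6^(21/30) = 30.1%

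If a fraction q of patients is stopped at day t, the overall rate falls by q times the difference. For R = 20% that is q × 10.1 points (t = 14) or q × 5.5 points (t = 21). For R = 40% it is q × 18.8 or q × 9.9 points. The protocol gives no q, so the loss runs from zero up to those figures. Complications that cluster early after surgery would lose less.

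With 25 patients in the denominator, each patient whose only event is missed moves a rate by 1/25 = 4 points.

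**5. Link to the surgical complication rate**

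Section 9.2.4 describes this endpoint as a proportion of patients who completed surgery. It names no complication, period or data source. Apart from chest X-rays on the first post-operative day and at one month (footnote 14), the AE row is the only general event collection in Table 1. It is therefore plausible, but not stated, that complications come from AE records.

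**The case against.** The best defence is that the stop is a deliberate choice: it keeps the toxicity of later drugs out of lorlatinib's profile. That has merit for drug-attributed tables, but a flag for onset after new therapy serves the same purpose without discarding post-operative events.

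It can also be said that the protocol plans AE review at about one month even in patients on further therapy (Section 6.4.6 and the later part of footnote 13). That is true, and it means shortened recording is not the protocol's settled effect. It does not remove the conflict with Section 8.1.

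The bias may be small. If patients who recover well start therapy first, the stop falls on those with the fewest complications left to record. This stands, and is one reason why no size can be claimed.

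Several stronger readings are tempting, and the documents do not support them:

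- *Every patient has a different window.* Those who start no new therapy before the final visit share one.
- *Patients leave the study before the one-month visit by design.* That is one reading of the preposition in "will conclude their participation in this study within 1-month post-surgery". Table 1, Sections 6.4.6 and 6.4.7 and another sentence of Section 3.1 all point to follow-up to about one month, so this is a wording conflict.
- *Section 8.11.2 contradicts Section 8.1.* It repeats the general rule that stands in Section 8.1 before the exception, and the two can be read together.
- *The surgical complication rate is shown to be biased.* The link to AE records is an inference.
- *A share of calendar days lost equals a share of complications lost.* That would need events spread evenly over the month, which the protocol does not state.
- *Patients who switch therapy before surgery are a further gap.* New systemic anticancer therapy is a listed reason for withdrawal (Section 6.4.8), so the protocol does not clearly keep them on the surgical path.

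**Conclusion.** The point holds in limited form. Sections 8.1 and 3.1 (Table 1, footnote 13) stop non-serious AE recording at the start of new anticancer therapy. The protocol lets that therapy begin during the month after surgery and also schedules AE collection at the end of that month. Followed as written, the stop can give some patients a shorter post-surgical window than others and undercount non-serious post-operative events in the safety and tolerability tables. The same applies to the surgical complication rate only if it is taken from AE records, which Section 9.2.4 leaves open.

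The direction is downward or nil. The size cannot be derived from the protocol: it depends on how many patients start therapy within a month, when they start, and how complications are distributed in time. The percentages under the assumed 20% to 40% rates show the mechanism and are not estimates for this trial. The primary endpoint is not affected. The change is worth making because it is cheap and removes a contradiction that sites would otherwise have to resolve themselves.

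**What to change.** - In Section 8.1 and Table 1, footnote 13, record non-serious AEs through the visit one month after surgery, whatever anticancer therapy has started. Carry the same end point into Section 8.11.2.
- Add one CRF flag for onset after the start of new anticancer therapy, so that lorlatinib-attributed tables can exclude those events.
- In Section 9.2.4, define the surgical complication rate as the proportion of operated patients with at least one complication over that same fixed window.
- Reconcile the wording in the synopsis (Methods) and Section 3.1 that ends participation within a month of surgery with the follow-up statement in Section 3.1, Table 1, and Sections 6.4.6 and 6.4.7.

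The cost is a wording amendment and one CRF field. The downside is that some AEs of later drugs will be recorded and must be tabulated separately. These changes do not alter the SAE window, which is tied to the last dose and can close before surgery. If the complication rate is to include serious events, their collection over the same window must also be secured.

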## **8.2 Definition of an Adverse Event**

An AE is any untoward medical occurrence in a clinical investigation during which a subject is administered a product or medical device; the event need not necessarily have a causal relationship with the treatment or usage. Examples of AEs include but are not limited to:

- Abnormal test findings;
- Clinically significant symptoms and signs;
- Changes in physical examination findings;
- Hypersensitivity;
- Drug abuse;
- Drug dependency.

Additionally, they may include the signs or symptoms resulting from:

- Drug overdose;
- Drug withdrawal;
- Drug misuse;
- Drug interactions;
- Exposure during pregnancy;
- Exposure via breast-feeding;
- Medication error.

Worsening of signs and symptoms of the malignancy under study should be reported as AEs in the appropriate section of the CRF. Disease progression assessed by measurement of malignant lesions on radiographs or other methods should not be reported as an AE.

## 8.3 Abnormal Test Findings

The criteria for determining whether an abnormal objective test finding should be reported as an AE are as follows:

- Test result is associated with accompanying symptoms, and/or
- Test result requires additional diagnostic testing or medical/surgical intervention, and/or
- Test result leads to a change in study dosing or discontinuation from the study, significant additional concomitant drug treatment, or other therapy, and/or
- Test result is considered an AE by the investigator.

Merely repeating an abnormal test, in the absence of any of the above conditions, does not constitute an AE. Any abnormal test result that is determined to be an error does not require reporting as an AE.

## 8.4 Serious Adverse Events

A SAE is any untoward medical occurrence at any dose that:

- Results in death;
- Is life-threatening (immediate risk of death);
- Requires inpatient hospitalization or prolongation of existing hospitalization;
- Results in persistent or significant disability/incapacity (substantial disruption of the ability to conduct normal life functions);
- Results in congenital anomaly/birth defect.

Progression of the malignancy under study (including signs and symptoms of progression) should not be reported as a SAE unless the outcome is fatal within the safety-reporting period. Hospitalization due to signs and symptoms of disease progression should not be reported as a SAE. If the malignancy has a fatal outcome during the study or within the safety-reporting period, then the event leading to death must be recorded as an AE and as a SAE with CTCAE Grade 5 (see Section 8.6).

Medical and scientific judgment is exercised in determining whether an event is an important medical event. An important medical event may not be immediately life-threatening and/or result in death or hospitalization. However, if it is determined that the event may jeopardize the subject or may require intervention to prevent one of the other AE outcomes, the important medical event should be reported as serious.

Examples of such events are intensive treatment in an emergency room or at home for allergic bronchospasm; blood dyscrasias or convulsions that do not result in hospitalization; or development of drug dependency or drug abuse.

#### **8.4.1 Potential Cases of Drug Induced Liver Injury**

Abnormal values in AST and/or ALT concurrent with abnormal elevations in total bilirubin that meet the criteria outlined below in the absence of other causes of liver injury are considered potential cases of drug-induced liver injury (potential Hy's Law cases) and should always be considered important medical events.

The threshold of laboratory abnormalities for a potential case of drug-induced liver injury depends on the subject's individual baseline values and underlying conditions. Subjects who present with the following laboratory abnormalities should be evaluated further to definitively determine the etiology of the abnormal laboratory values:

- Subjects with AST or ALT and total bilirubin baseline values within the normal range who subsequently present with AST or ALT  $\geq 3$  times ULN concurrent with a total bilirubin  $\geq 2$  times ULN with no evidence of hemolysis and an alkaline phosphatase  $\leq 2$  times ULN or not available.
- For subjects with pre-existing AST or ALT or total bilirubin values above ULN, the following threshold values should be used in the definition mentioned above:

- For subjects with pre-existing AST or ALT baseline values above the normal range:  
AST or ALT  $\geq 2$  times the baseline values and  $\geq 3$  times ULN, or  $\geq 8$  times ULN (whichever is smaller).

concurrent with

- For subjects with pre-existing values of total bilirubin above the normal range:  
Total bilirubin of  $\geq 2$  times ULN and increased by  $>1$  time the ULN or  $\geq 3$  times ULN (whichever is smaller) with no evidence of hemolysis and an alkaline phosphatase  $\leq 2$  times ULN or not available.

The subject should return to the investigational site and be evaluated as soon as possible, preferably within 48 hours from awareness of the abnormal results. This evaluation should include laboratory tests, detailed history and physical assessment and the possibility of hepatic neoplasia (primary or secondary) should be considered. In addition to repeating AST and ALT, laboratory tests should include albumin, creatinine kinase, total bilirubin, direct and indirect bilirubin, gamma-glutamyl transferase, prothrombin time, international normalized ratio, and alkaline phosphatase. A detailed history, including relevant information, such as review of ethanol, acetaminophen, recreational drug and supplement consumption, family history, occupational exposure, sexual history, travel history, history of contact with a jaundiced patient, surgery, blood transfusion, history of liver or allergic disease, and work exposure, should be collected. Further testing for acute hepatitis A, B, or C infection and liver imaging (e.g., biliary tract) may be warranted. All cases confirmed on repeat testing as meeting the laboratory criteria defined above, with no other cause for liver function test abnormalities identified at the time should be considered potential Hy's Law cases irrespective of availability of all the results of the investigations performed to determine etiology of the abnormal liver function tests.

Such potential Hy's Law cases should be reported as SAEs.

